8.2 Safety and Other Assessments

The investigational device is not being evaluated for safety as a primary endpoint in this clinical study.

8.3 Adverse Events and Serious Adverse Events

8.3.1 *Definition of Adverse Events (AE)*

An adverse event is any undesirable experience associated with the use of a medical product in a subject. No adverse events are expected since the device is of nonsignificant risk. The device does not introduce energy to the patient. In addition, voltages related to the device electronics are regulated via appropriate circuitry on board the device.

8.3.2 *Definition of Serious Adverse Events (SAE)*

Not applicable.

8.3.3 *Unanticipated Adverse Device Effect (UADE)*

A UADE is any serious adverse effect on health or safety, or any life-threatening problem or death caused by, or associated with, a device, if that effect, problem, or death was not previously identified in nature, severity, or degree of incidence in the investigational plan or application, or any other unanticipated serious problem associated with a device that relates to the rights, safety, or welfare of subjects.

8.3.4 *Classification of an Adverse Event*

8.3.4.1 *Severity of Event*

Not applicable, no adverse events are defined given the minimal risk of device intervention.

8.3.4.2 *Relationship to Study Intervention*

Not applicable, no adverse events are defined given the minimal risk of device intervention.

8.3.4.3 *Expectedness*

The principal investigator will be responsible for determining whether an adverse event (AE) is expected or unexpected. An AE will be considered unexpected if the nature, severity, or frequency of the event is not consistent with the risk information previously described for the investigational device. However, once again, no adverse events are expected with the described device intervention.

8.3.5 *Time Period and Frequency for Event Assessment and Follow-Up*

No adverse events are expected related to the device, device intervention procedure, or study as a whole. As such, no follow-ups will take place.

8.3.6 *Adverse Event Reporting*

No such reporting will occur given that no adverse events are expected or reasonably probable. In the highly unlikely case of an AE, it will be reported to the principal investigator. The principal investigator will subsequently submit appropriate documentation to the IRB within a timely fashion, as dictated by Penn IRB policy.

8.3.7 *Serious Adverse Event Reporting*

See previous section.

8.3.8 *Reporting Events to Participants*

Not applicable.

8.3.9 *Events of Special Interest*

Not applicable.

8.3.10 *Reporting of Pregnancy*

Pregnancy, in and of itself, is not regarded as an AE as there is no additional risk to the subject and no risk to the fetus.

8.4 *Unanticipated Problems*

8.4.1 *Definition of Unanticipated Problems (UP)*

The Office for Human Research Protections (OHRP) considers unanticipated problems involving risks to participants or others to include, in general, any incident, experience, or outcome that meets all the following criteria:

- Unexpected in terms of nature, severity, or frequency given (a) the research procedures that are described in the protocol-related documents, such as the Institutional Review Board (IRB)-approved research protocol and informed consent document; and (b) the characteristics of the participant population being studied;
- Related or possibly related to participation in the research (“possibly related” means there is a reasonable possibility that the incident, experience, or outcome may have been caused by the procedures involved in the research); and
- Suggests that the research places participants or others at a greater risk of harm (including physical, psychological, economic, or social harm) than was previously known or recognized.

8.4.2 *Unanticipated Problem Reporting*

Unanticipated problems (UPs) such as the following should be reported to the principal investigator:

- Complaint of a participant when the complaint indicates unexpected risks, or the complaint cannot be resolved by the research team
- Breach of confidentiality
- Premature closure of a study (e.g., due safety, lack of efficacy, feasibility, financial reasons, etc.)

The UP report will include the following information:

- Protocol identifying information: protocol title and number, PI’s name, and the IRB project number;
- A detailed description of the event, incident, experience, or outcome;
- An explanation of the basis for determining that the event, incident, experience, or outcome represents an UP;
- A description of any changes to the protocol or other corrective actions that have been taken or are proposed in response to the UP.

To satisfy the requirement for prompt reporting, UPs will be reported using the following timeline:

- Any other UP will be reported to the principal investigator within 48 hours of the study team member becoming aware of the problem.

All UPs should be reported to appropriate institutional officials (as required by an institution’s written reporting procedures), the supporting agency head (or designee), and the Office for Human Research Protections (OHRP) within 48 hours of the IRB’s receipt of the report of the problem from the investigator.

8.4.3 Reporting Unanticipated Problems To Participants

Not applicable.

8.5 Device Reporting

Safety reporting for the device will be according to 21 CFR 812.150.

9 STATISTICAL CONSIDERATIONS

9.1 Statistical Hypotheses

Not applicable.

9.2 Sample Size Determination

A sample size of 30 patients was determined based on the frequency of patients expected to undergo lung resection at the Hospital of the University of Pennsylvania and Presbyterian Medical Center, receive an incentive spirometer during their postoperative stay, and fit the study inclusion criteria within a 3 month period.

9.3 Populations for Analyses

The population will include adult patients.

9.4 Statistical Analyses

9.4.1 General Approach

The data collected from the digital incentive spirometer for an individual patient, which will include timestamps of inspiratory attempts and inspiratory volume, will first be screened for false readings which are defined as an inspiratory attempt for which an inspiratory volume is ≤ 100.0 mL. False readings may occur from improper use of the device or the patient being interrupted during an inspiratory attempt, and will not be included in the analysis. To determine the total incentive spirometry adherence for a patient, the number of inspiratory breath attempts performed with the digital IS per day will be calculated and then averaged across the length of the patient's visit (or number of days the IS was in use). To determine the consistency of incentive spirometry adherence throughout postoperative stay, the number of 1 hour intervals in which at least one inspiratory breath was attempted using the digital IS will be calculated and represented as a percent of the total number of hours the digital IS was powered on and recorded metrics.

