1 STUDY SUMMARY

1.1 Synopsis

Title:	Airalux Digital Incentive Spirometer
Short Title:	Digital Incentive Spirometer
Study Description:	This single-arm proof-of-concept research study aims to assess the effect of a digital incentive spirometer (IS) device and a companion mobile-based app on incentive spirometry adherence in patients post-surgery. The digital IS utilizes a sensor to measure inspiratory breaths, and these data are transmitted wirelessly to a secure cloud database. The spirometer and app include a patient reminder system, exercise gamification strategies, progress tracking, and additional features designed to promote patient IS use.
Objectives:	The objective of this study is to evaluate the effect of a digital IS that provides gentle auditory and haptic reminders and exercise guidance on patient adherence to incentive spirometry. Secondarily, this study will evaluate metrics relating to lung function to assess post-surgery lung recovery in patients using the digital IS.
Primary Endpoint:	Total incentive spirometry adherence - Number of inspiratory breath attempts performed with the digital IS per day. Consistency of incentive spirometry adherence throughout postoperative stay - Percent of recorded hours in which at least one inspiratory breath was attempted using the digital IS.
Secondary Endpoints	Quality of inspiratory breaths attempted with the digital IS - quality refers to inspiratory volumes achieved. Blood oxygen saturation - Postoperative SpO2 Pain Scores - Postoperative pain scores will be reported on a scale from 0 (no pain) to 10 (unbearable pain). Pulmonary function testing lab results – preoperative spirometry results from pulmonary function lab

Study Population:	
30 patients (of adult categorization) undergoing anatomic lung resection surgery and receive an incentive spirometer as standard-of-care. No restriction on gender, demographic group, or geographic location.
 
We will be enrolling patients that receive surgery from [name] (Principal Investigator), [name] (Chief of Thoracic Surgery), and/or [name] (Chief of Surgery, PPMC) at the sites listed below.

Phase:	Exploratory

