Description of Sites/Facilities	
Hospital of the University of Pennsylvania, [name]
 
Penn Medicine Valley Forge, [name]
 
Penn Medicine University City, [name]
 
Penn Medicine Cherry Hill, [name]
 
Penn Thoracic Surgery Presbyterian, Presbyterian Medical Center of the University of Pennsylvania, [name]
 
Perelman Center for Advanced Medicine, [name]

Enrolling Sites:	
Hospital of the University of Pennsylvania, [name]
 
Penn Medicine Valley Forge, [name]
 
Penn Medicine University City, [name]
 
Penn Medicine Cherry Hill, [name]
 
Penn Thoracic Surgery Presbyterian, Presbyterian Medical Center of the University of Pennsylvania, [name]
 
Perelman Center for Advanced Medicine, [name]

Description of Study Intervention:	
Patients will be instructed to periodically perform inspiratory breaths from the mouthpiece of the digital IS device during their postoperative stay similar to how standard-of-care incentive spirometers are instructed. The digital IS utilizes a sensor to measure inspiratory flow rates and volumes. These data will be displayed to the patient during inspiratory breaths on the device screen. The screen and a speaker in the device along with the mobile

	app will provide visual and auditory cues to guide patients in performing inspiratory breaths and periodically remind patients to perform them.
Study Duration:	Estimated length of time to enroll all subjects and complete the study: 3 months.
Participant Duration:	For the entirety of a patient's postoperative hospital stay until they are discharged (on average 2-3 days) or up to 1 week post-surgery.

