1.2 Key Roles and Study Governance

Sponsor	Medical Director
N/A, principal investigator-initiated study	[name]
	Division of Thoracic Surgery, Hospital of the University of Pennsylvania
	[name]
	[contact]
	[contact]

- 1.3 Schema

Office (within 1-30 days prior to surgery) - Informed Consent

- Obtain informed consent alongside surgery consent
- (Optional) Obtain patient or family member email address (linked to their Apple ID) to approve access to the Airalux app on their App Store (IOS only)
 - The Airalux app provides guided IS exercise sessions, allows patients and family members to view past IS exercise measurements, and gamifies adherence metrics.

Pulmonary function lab – Spirometry Testing

- Patients will receive spirometry testing at the pulmonary function lab. This is part of routine care. This is not a study intervention.

Pre-op holding (morning of surgery) - Baseline Measurement

- Patients receive the Airalux device and use it to perform a baseline IS measurement
- Research team records the device identification key of the device that the patient is receiving
- (Optional) For patients with the Airalux app, they can sign in to the app with their device identification key.

Post-anesthesia care unit (2-4 hours post-surgery) - Study Intervention Administered

- Patients are instructed to perform IS exercises with their device
- The device will gently vibrate/buzz every 15 minutes to prompt patients to complete an IS exercise
- (Optional) Patients can follow guided exercises on the app if desired

Inpatient hospital floor (0-7 days post-surgery) - Study Intervention Administered, Collection of Endpoints

- Patients are instructed to perform IS exercises with their device throughout their hospital stay
- The device will vibrate every 15 minutes to prompt patients to complete IS exercise
- (Optional) Patients can follow guided exercises on the app if desired
- Patient pulse oximetry data is collected every 4 hours. This is part of routine care. This is not a study intervention.
- Patient pain scores are collected at minimum every 12 hours (at least once per shift). This is part of routine care. This is not a study intervention.

Discharge - Study Ends (conclusion of hospital stay)

- Patients will not be able to use the Airalux device outside of the hospital
- Patients will receive a standard of care incentive spirometer to use at home

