6 STUDY INTERVENTION

6.1 Study Intervention(s) Administration

6.1.1 *Study Intervention Description*

The device intervention being utilized in this study is a handheld digital IS composed of the following components:

- Disposable mouthpiece and airflow tube, made of biocompatible, non-conductive plastic (PLA, TPU) and/or dental resin (size: 1 in. x 1 in. x 0.5 in), and the following electronics
 - Ported pressure sensor
- Device body, made of biocompatible, non-conductive plastic material (PLA) that encases the following electronics which do not come in contact with the patient (size: 7 in. x 2 in. x 2.5 in)
 - Rechargeable Lithium-Ion battery (an off-the-shelf consumer power bank)
 - Anker Nano Power Bank with Built-in Foldable USB-C Connector, 5,000mAh Portable Charger 22.5W
 - Speaker with an output wattage of up to 2W
 - LED display screen (1.3 in diagonal)
 - Digital signal processing microcontroller
 - Coin vibration motor
 - Momentary push button

- Wiring, coated in non-conductive casing

The study intervention also includes a mobile application that can be downloaded to a portable smart device such as a smartphone or tablet.

The digital IS will be used by the patient for the duration of their postoperative stay, turned on each morning after the patient is awake, and turned off before the patient goes to sleep for the night. When turned on, the device will gently vibrate to prompt users every 15 minutes to remind patients to perform their prescribed breathing exercises.

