12 APPENDIX

12.1 Schedule of Activities (SoA)

Procedures	Day 0	0-30 day waiting period	Day 1 (day of surgery)	Day 2-7 (remainder of postoperative stay)
Informed consent	X			
Perform baseline measurement of inspiratory volume			X	
Administer study intervention and collection of study endpoints and patient survey			X	X

END OF DOCUMENT

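### Breaths per day (9.4.1) is not adjusted for the part-days of surgery and discharge, and its two permitted denominators give different answers

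*Combined protocol and SAP*

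**What the plan says.** The Synopsis defines the first primary endpoint as "Number of inspiratory breath attempts performed with the digital IS per day". Under 9.4.1 the number of attempts "per day will be calculated and then averaged across the length of the" patient's visit; a parenthesis there offers the number of days of use as the alternative denominator. The section does not say what a day is, which of the two denominators applies, or how an incomplete day is treated. Section 9.4.2 then reports the mean and standard deviation over all patients.

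Other sections set how long the device is available:

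- **Start.** The Schema (1.3) has the entry "Post-anesthesia care unit (2-4 hours post-surgery) - Study Intervention Administered". The Schedule of Activities (12.1) numbers the day of surgery as Day 1 and marks endpoint collection on it.
- **Nights.** Under 6.1.1 the device is "turned on each morning after the patient is awake, and turned off before the patient goes to sleep for the night".
- **End.** The Schema states: "Patients will not be able to use the Airalux device outside of the hospital".
- **Length.** Participation lasts "until they are discharged (on average 2-3 days) or up to 1 week post-surgery" (Synopsis, Participant Duration).

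The second primary endpoint, consistency, is handled differently in the same paragraph of 9.4.1: it is a percentage of the hours in which the device was on and recording.

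**The concern.** The day of surgery and the day of discharge are normally part-days, yet averaging daily counts gives each the weight of a full waking day. A patient who stays two nights contributes three counts, two of them from part-days. One who stays three nights contributes four, again with two from part-days. Patients with the same hourly use can therefore get different primary values because of how long they stayed and when they were operated on and discharged.

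The choice of denominator adds to this. Length of visit may mean calendar days or elapsed time, and a day without use counts towards the visit but not towards days in use. The day-exclusion rule in 9.4.2 does not settle the matter. It does not name part-days, and its open-ended clause about other events could be read to keep or to drop them, a choice that could then be made after the data are seen.

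A smaller gap concerns the baseline. It is taken before surgery on Day 1 with the same device, and 6.4 indicates that it appears in the time-stamped data. Section 9.4.1 does not explicitly limit the attempt count to the postoperative period.

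Because the study has no comparator and no test, this mean and standard deviation are themselves the primary result.

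**Working it through.** There is no planned figure to reproduce. The 30 patients in 9.2 come from expected patient flow, and no value or SD is given for this endpoint. The check is how far the reported value departs from a patient's own full-day rate.

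**Inputs from the documents:** use starts 2-4 hours after surgery on Day 1, the device is off overnight, use ends at discharge, the average stay is 2-3 days, and prompts come every 15 minutes.

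**Assumptions (not in the documents):** constant hourly rate; waking day W = 16 h (14 h as a check); device hours a = 2-10 on the day of surgery and b = 2-8 on the day of discharge. A stay of 2-3 nights is taken as D = 3-4 calendar days.

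**Averaging daily counts.** Reported value divided by full-day rate:

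f = (a + b + (D − 2)·W) / (D·W)

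| Calendar days D | Shortest part-days (2 h, 2 h) | Longest part-days (10 h, 8 h) |
|---|---|---|
| 2 | 4/32 = 0.13 | 18/32 = 0.56 |
| 3 | 20/48 = 0.42 | 34/48 = 0.71 |
| 4 | 36/64 = 0.56 | 50/64 = 0.78 |
| 7 | 84/112 = 0.75 | 98/112 = 0.88 |

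With W = 14 the ranges are 0.43-0.76 for D = 3 and 0.57-0.82 for D = 4. Hence roughly 0.4-0.8 for 3-4 calendar days.

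**The denominators compared, one illustration.** Surgery ends 15:00, device in use from 18:00, awake 07:00-23:00, discharge 11:00. This gives 5 h on the first day and 4 h on the last. Elapsed time runs from end of surgery to discharge.

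| Nights | Device hours | Calendar-day ratio | Elapsed days | Elapsed-time ratio |
|---|---|---|---|---|
| 1 | 9 | 9/32 = 0.28 | 20/24 = 0.83 | (9/16)/0.83 = 0.68 |
| 2 | 25 | 25/48 = 0.52 | 44/24 = 1.83 | (25/16)/1.83 = 0.85 |
| 3 | 41 | 41/64 = 0.64 | 68/24 = 2.83 | (41/16)/2.83 = 0.90 |

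A patient who answers every prompt makes 4 × 16 = 64 attempts on a full day. Averaged over calendar days, this patient scores 36/2 = 18, 100/3 = 33 or 164/4 = 41 for one, two or three nights.

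**How much of the between-patient spread is timing?** Simulation of 400,000 patients: a uniform on 2-10 h, b uniform on 2-8 h, W = 16, and a lognormal true rate r with CV 0.2-0.8 (assumed, since no SD is given). Reported value y = r·f; share due to timing and stay = Var(log f)/Var(log y).

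- Stays of 2-3 nights: 29% at CV 0.2, falling to 3% at CV 0.8. Mean f is 0.62, which agrees with the hand values: (11 + 16)/48 = 0.56 and (11 + 32)/64 = 0.67, averaging 0.62.
- Stays of 1-2 nights (2-3 calendar days): 75% at CV 0.2, 57% at 0.3, 34% at 0.5, 19% at 0.8.

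**With exposure adjustment.** Attempts divided by device hours gives a ratio of 1.00 for any stay or timing, given a constant hourly rate.

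**The case against.** A reader might infer that the endpoint mostly reflects surgery and discharge timing. The documents do not support that. They give neither clock times nor a between-patient SD. In the simulation, timing and stay explain 3-29% of the log-variance for 2-3 night stays; they exceed half for 1-2 night stays only when the true-rate CV is about 0.3 or less.

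A reader might also take it as stated that part-days count as whole days. That is the natural reading of averaging daily counts, but it is not written. Length of visit can mean elapsed time, and the shortfall is then smaller.

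It can fairly be said that observed attempts per calendar day is a valid raw count, low only against a full waking day at a constant rate. It can also be said that no comparison with the daily exercise counts cited in 2.2 is planned, and the documents do not show how that trial treated part-days, so lost comparability is not part of this point. The baseline effect is small: the Schema lists the baseline separately and puts endpoint collection on the inpatient floor. Finally, the consistency endpoint is already exposure-based, and the time stamps would allow a rate to be computed later.

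These arguments limit the size and wording of the point. They do not supply a definition of the day, a choice of denominator or an adjustment for part-days.

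**Conclusion.** The point holds in moderate form and should be corrected before analysis. Section 9.4.1 leaves breaths per day unadjusted for part-days and allows two denominators that disagree. For stays of 3-4 calendar days, a patient's value is roughly 0.4-0.8 of the full-day rate if daily counts are averaged, and 0.85-0.90 in the one elapsed-time illustration. The effect is larger for shorter stays and smaller for a full week.

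These sizes rest on assumed part-day hours, a 14-16 hour waking day and a constant hourly rate. The direction of the daily-count result does not depend on the exact hours, provided the first and last days are shorter than a full waking day. The point concerns one of two primary endpoints in an exploratory, single-arm study without a test: the result depends partly on logistics, and how much cannot be fixed from the documents.

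**What to change.** In 9.4.1, fix one exposure-adjusted definition of total adherence per patient:

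- Divide postoperative attempts by available postoperative hours, counting attempts and hours over the same stated window, and multiply by a stated standard day. Alternatively, use powered-on recorded hours as the denominator, as the consistency endpoint already does.
- Where 9.4.2 excludes a day, remove both its attempts and its hours.
- Exclude attempts time-stamped before surgery, including the baseline measurement.
- Report plain daily counts separately for the day of surgery, full postoperative days and the day of discharge. This also shows whether the hourly rate differs between types of day, which a single rate would hide.

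The cost is about one paragraph. The window or standard day is a convention and must be stated with the result. Powered-on hours need no new data but do not capture time when the device was left off. A window running from PACU instruction to discharge avoids that, but those two times are not in the recorded-data lists in 10.1.3 and would have to be added; 10.1.8.1 already provides for taking clinical data from the hospital record.

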7 STUDY INTERVENTION DISCONTINUATION AND PARTICIPANT DISCONTINUATION/WITHDRAWAL

7.1 Discontinuation of Study Intervention

Discontinuation from protocol specified activities will result in discontinuation from the study. In this situation, the device is the only clinical intervention being utilized with patients. As such, discontinuing the use of the IS device prohibits data collection and renders the patient's data incomplete and therefore useless for analyses. Furthermore, there are no follow ups involved in this study so discontinuation from device intervention prevents collection of metrics associated with secondary endpoints and constitutes a patient's discontinuation from the study.

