8 STUDY ASSESSMENT AND PROCEDURES

8.1 Efficacy Assessments

Study Procedures and Evaluations:

- 1) Patient identification and eligibility screening:
 - a. Once a potential participant is identified as already scheduled for a lung resection surgery, the clinical team will determine whether the patient satisfies the eligibility criteria.
 - b. Any additional eligibility criteria that cannot be identified or evaluated via Penn Charts will be reviewed and confirmed by the clinical team following receipt of signed ICF forms.
- 2) Patient visit and informed consent:
 - a. If any additional eligibility criteria need to be screened due to a lack of information in Penn Charts, the patient will be asked relevant questions after providing necessary informed consent to the clinical team.
 - i. This will take place in the doctor's office that is private. Note that in-patient hospital stay will not be billed to the study as the hospital stay is unrelated to participation in the study.
- 3) Patient spirometry testing at the pulmonary function laboratory
 - a. This is already done as part of routine care. This is not a study intervention. Lab results from spirometry testing will be a secondary endpoint.
- 4) Device intervention during patient visit
 - a. After receiving informed consent, during preoperative holding, the clinical team will give the patient one digital IS, facilitate the download of the companion app onto the patient's personal mobile device if applicable, and obtain a baseline inspiratory volume measurement.
 - b. Post-surgery, the clinical team will teach patients how to perform breathing exercises with the digital IS and instruct them regarding the quantity, frequency, and volume of inspiratory breaths to perform throughout their hospital stay.
 - i. While the digital IS is powered on, an auditory and haptic reminder will occur every 15 minutes to remind the patient to perform their breathing exercises. The patient has full autonomy as to when and how often to use the digital IS. Digital IS usage and inspiratory volume data will be collected by the device whenever it is used by the patient.
 - ii. At minimum twice per day, the clinical team will collect pain scores. This is already done as part of routine care. This is not a study intervention.

- iii. Every 4 hours, the clinical team will record a patient's SpO2. This is already done as part of routine care. This is not a study intervention.

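### The breaths-per-day primary endpoint has two denominators and no rule for choosing; the days-in-use option can drop days when the device was available but unused

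*Combined protocol and SAP*

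**What the plan says.** Section 9.4.1 forms the total-adherence endpoint in two steps. Attempts are counted for each day, and the daily counts are then averaged over the length of the "visit (or number of days the IS was in use". The synopsis and section 3 define the endpoint only as attempts per day. Neither they nor section 9.4.1 say which denominator applies, what being in use means, or how a day is delimited.

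These sections bear on the point:
- Section 8.1: "The patient has full autonomy as to when and how often to use the digital IS".
- Section 6.1.1: the device is to be "turned on each morning after the patient is awake" and used throughout the post-operative stay.
- Section 7.1: data from a patient who discontinues the device are "incomplete and therefore useless for analyses".
- Section 9.4.2: a day is excluded when breath data could not be collected or were unreliable, for listed reasons and an open-ended group of other events.
- Section 9.4.1, consistency endpoint: hours with at least one attempt, as a percentage of the hours the device was powered on and recording.
- Synopsis, participant duration: "on average 2-3 days) or up to 1 week post-surgery".
- Sections 1.3 and 12.1: use begins in the "Post-anesthesia care unit (2-4 hours post-surgery"), and the schedule labels the surgery day "Day 1 (day of surgery").

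**The concern.** A day on which a working device was within reach and the patient did not use it is the plainest form of non-adherence. Under the visit-length denominator that day counts as zero and lowers the patient's average. Under the days-in-use denominator it can disappear, and the average is then higher than the patient's behaviour over the stay.

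With stays of two to three days on average, one day is a large share of the denominator. If the choice is left open, it will be made after the data have been seen, on a study whose whole primary result is a mean and an SD. How the shortened surgery and discharge days enter the average is also unstated.

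**Working it through.** **Plan's own figure.** There is none to reproduce. Section 9.2 sets 30 patients from expected patient flow, with no effect size, SD, alpha or power.

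**Step 1: what happens to an available day without attempts.**

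| Day | Visit length | In use = powered on | In use = at least one breath | Consistency endpoint |
|---|---|---|---|---|
| Device off all day | counted as 0 | dropped | dropped | no hours enter, so not seen |
| Device on, no breaths | counted as 0 | counted as 0 | dropped | hours enter and lower the percentage |

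A device-off day is lost under either meaning of in use. A device-on day without breaths is lost under only one.

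**Step 2: effect on one patient.** Let T be total attempts, L the days of stay, and one day unused. The visit-length value is T/L and the days-in-use value is T/(L-1). The ratio is L/(L-1), whatever T is and whichever day is unused.
- L = 2: 2/1 = 2.00
- L = 3: 3/2 = 1.50
- L = 4: 4/3 = 1.33
- L = 7: 7/6 = 1.17

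For scale only, take the 35.4 daily exercises quoted in section 2.2 as the count on each used day. A 3-day patient with one unused day scores 35.4 × 2/3 = 23.6 or 35.4. A 2-day patient scores 35.4 × 1/2 = 17.7 or 35.4.

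**Step 3: effect on the mean of 30.** The documents give no frequency of unused days, so it is assumed. With 3-day stays, equal counts on used days, and k of 30 patients having one dropped day, the ratio of means is 1/(1 - k/90).
- k = 1: 90/89 = 1.011
- k = 3: 90/87 = 1.034
- k = 9: 90/81 = 1.111

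Unequal days move these figures. Assume 3 attempts an hour and 6, 14 and 3 usable hours on the surgery, full and discharge days. Daily counts are then 18, 42 and 9, a total of 69, or 23.0 per day. With k = 3:
- Full day unused: (27 × 23 + 3 × 9)/30 = 21.60 against (27 × 23 + 3 × 13.5)/30 = 22.05, up 2.1%.
- Surgery day unused: 22.40 against 23.25, up 3.8%.
- Discharge day unused: 22.70 against 23.70, up 4.4%.

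The same calculation gives 0.7% to 1.5% for k = 1 and 7.2% to 13.6% for k = 9.

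**Step 4: whether the consistency endpoint compensates.** Suppose the device is on h hours a day, with attempts in m of them, on two days of a 3-day stay, and is off on the third. The endpoint is 2m/2h = m/h, the same as for a patient with that pattern on all three days. If the device were on but unused on the third day, the value would be 2m/3h. The endpoint registers the second case and misses the first.

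**The case against.** The strongest reply is that the bracket is harmless. It may only acknowledge that the denominator shortens when section 9.4.2 excludes a day, or when a stay runs past one week. In most patients the two denominators coincide, because the device is meant to be switched on every morning, and section 7.1 deals with patients who stop. This is a fair account of what may have been intended. But the bracket does not limit itself to those cases, section 7.1 concerns discontinuation, and section 8.1 lets a continuing patient leave the device unused.

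It is also fair that section 9.4.2, on its better reading, does not exclude a voluntary day without use: a working device with no attempts gives a reliable zero. Its open-ended wording still needs tightening.

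Finally, the study is exploratory and descriptive, and stored time stamps allow recalculation. That limits the harm, but time stamps alone do not show whether an empty day reflects choice, device failure or inability.

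Three stronger readings are tempting and not supported:
- That the plan removes exactly the non-adherent days. This needs in use to mean at least one breath, and days of low but non-zero use stay in under every reading.
- That attempts might be divided by elapsed time in hospital, changing every patient's value. The two-step wording of section 9.4.1 points to days of equal weight; only the handling of partial days is open.
- That pre-operative attempts contaminate the count. Section 1.3 has a separate step, "Patients receive the Airalux device and use it to perform a baseline IS measurement", and sections 6.4 and 9.4.3 also treat it as a distinct measurement.

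**Conclusion.** The concern holds as an unresolved denominator for a primary endpoint, and it should be settled before the data are analysed. The days-in-use option certainly drops device-off days and possibly also device-on days without breaths. In both cases it raises measured adherence. The per-patient factor L/(L-1) is exact for one dropped day. The effect on the 30-patient mean is not known: it is about 1% if one patient is affected and roughly 7% to 14% if nine are, under the assumed 3-day stays and breath rates.

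A reader might infer that the primary result is already biased or that the study's inference is at risk. The documents support neither. The visit-length option keeps these days as zeros, section 9.1 states no hypotheses, and no test, error rate or sample size depends on the choice. What is affected is the reported mean and SD, and their interpretation as adherence.

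**What to change.** In section 9.4.1, delete the bracketed alternative. Keep the endpoint as post-operative attempts per calendar day, averaged over all post-operative days up to discharge or the 1-week cap, whichever comes first. State that an available day without attempts counts as zero.

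In section 9.4.2, limit day exclusions to documented device failure or documented inability to use the device, and remove those days from both numerator and denominator.

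State how the partial surgery and discharge days count. One option is a primary average over all calendar days, with a sensitivity analysis that omits the partial days or weights days by time available.

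The cost is a few sentences and a simple log of device failure or inability to use. The discharge date should be added to the recorded data listed in section 10.1.3, which does not name it; without it, unused days at the end of a stay cannot be identified from device data. No extra patients or patient procedures are needed. The downside for the study team is that reported adherence may be slightly lower.
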